Following the titration phase, patients whose arrhythmia was successfully suppressed will be randomized to the successful therapy or to a matching placebo. Patients whose arrhythmia was not successfully suppressed (though not included in the primary analyses) will be randomized to the best

therapy, that which is most effective among those which are tolerated and which do not increase the VPD rate, or to a matching placebo. During titration, suppression will be defined as $\geq 80\%$ reduction in the VPD rate and $\geq 90\%$ suppression of runs of VT (3-14 VPD's at a rate ≥ 120 per minute).

D. Endpoints

The primary endpoint in the suppression trial will be arrhythmic death as defined below.

Arrhythmic death is defined as (1) death occurring in less than 24 hours from the onset of new symptoms in the absence of severe left ventricular failure or shock which in itself might have been expected to cause death; (2) resuscitated ventricular fibrillation (or, if no rhythm documentation is available, resuscitated cardiac arrest; i.e., resuscitated ventricular tachycardia is not to be counted as an "arrhythmic death"); (3) unwitnessed death without other known noncardiac causes.

In the absence of documentation to the contrary, death occurring in < 24 hours from onset of symptoms will be considered to be a sudden arrhythmic death as long as the only new symptoms were ischemic pain or pressure, syncope, palpitations or dizziness, and as long as the patient died of documented or presumed arrhythmia. Death which occurs as the end result of CHF/shock, even though occurring in < 1 hour from onset of symptoms, will not be considered to be sudden arrhythmic death. In circumstances where the event is witnessed but poorly documented, or for other cardiac conditions, death or cardiac arrest which occurs within 1 hour of onset of symptoms will be considered to be arrhythmic. If any symptoms are separated from onset of death/cardiac arrest by a symptom-free period of 24 hours, then these symptoms will not be considered as part of the death/cardiac arrest event itself.

Secondary endpoints will include:

- (1) total cardiac mortality
- (2) the combination of sustained ventricular tachycardia and arrhythmic death
- (3) total overall mortality (both cardiac and non-cardiac)

Additional objectives of the study will be to evaluate:

- (1) the relationship of baseline ejection fraction to the primary and secondary endpoints

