- (2) the relationship of the time at which drug therapy is initiated to the primary and secondary endpoints
- (3) the relationship of other baseline characteristics to the primary and secondary endpoints
- (4) suppressable versus unsuppressable patients
- (5) the effect of antiarrhythmic therapy on congestive heart failure

Primary analyses will be by intention to treat and will be one-sided, with an alpha value of 0.025. Safety (adverse effects, including potential proarrhythmia) will be monitored by the Data and Safety Monitoring Board.

E. Duration and Estimated Sample Size

Patients will be enrolled for three years, and all patients will be followed to a common termination date, which will be two years beyond enrollment of the last patient. It is expected that 4400 patients will be enrolled into the main study during this period. This number will provide a power of at least 85% to detect a 30% reduction in arrhythmic death. It is expected that 800 to 1200 patients will be enrolled into the substudy of patients with inadequate suppression of VPD's. Because the incidence of arrhythmic death in these patients is unknown, power calculations are problematical. Details of the sample size calculations are included in Appendix 1.

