During followup, temporary or permanent suspension of study medication will be allowed for certain procedures and events. In the absence of contraindications, the drugs will then be restarted. The specifics for each of the events are noted below.

The specific events which would require permanent withdrawal of the study drug for institution of treatment with other antiarrhythmic agents during followup include 1) resuscitated cardiac arrest or ventricular fibrillation, 2) sustained (symptomatic or asymptomatic) ventricular tachycardia (≥ 15 complexes at ≥ 120 beats per minute), and 3) symptomatic (hemodynamically important) unsustained ventricular tachycardia.

1. Resuscitated cardiac arrest or ventricular fibrillation.
The Death or Cardiac Arrest form must first be completed. Only, if it is absolutely necessary, should the drug code be broken, and in no case should it be broken before the form is completed. Such patients may be appropriate for an ancillary study; no additional study followups need be scheduled and no further CAST data should be collected.
2. Disqualifying (symptomatic or asymptomatic) ventricular tachycardia (≥ 15 complexes at ≥ 120 beats/min.)
The VT form must be completed. Only if it is absolutely necessary (i.e., if required by the private physician or CAST physician) should the drug code be broken, and in no case before the form is completed. The patient will proceed to individualized therapy or a substudy as appropriate. Followup will be completed per schedule.
3. Symptomatic (hemodynamically important) unsustained ventricular tachycardia.
Such symptoms include a) syncope; b) one of the following when probably caused by arrhythmia-related hypoperfusion: presyncope, lightheadedness, dizziness, weakness or diaphoresis; c) one of the following when probably caused by arrhythmia-related hypoperfusion of the heart: shortness of breath or chest pain. Those arrhythmias which only manifest themselves by palpitations are not included. The patient will proceed to individualized therapy or a substudy. If the physician demands, the code may be broken to assist in individualized therapy decisions, but if so the VT form should be completed first. The patient will be followed per protocol.

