In general, the investigators will attempt to keep patients in CAST with adequate suppression of arrhythmia. For some events, it will not be possible to remain blinded to the therapy or to continue titration. For certain other events, it will be both possible and desirable to change drugs or doses. In such cases where titration is continued, the patient will resume titration with active drug or with placebo depending on the CAST assignment. Therapy will be assigned by the Coordinating Center so the investigator and patient will be blinded. When it appears that adequate resolution of arrhythmias or adverse effects has occurred, the patient will continue on that therapy and a Holter obtained which will not be read locally. The Holter will be used for safety and to document the level of suppression. In no case will the patient be allowed to return to a specific drug once he has proceeded to the next drug in the titration scheme. In addition, a patient advanced to individualized therapy will still be followed per protocol. If a drug code is broken (unblinded), as few individuals as possible will be informed about the unblinded therapy. Likewise, if a drug code is to be broken (unblinded), pertinent event forms must be completed before the code is broken.

At the end of study, the code will be broken. The patient's status may then be reviewed with respect to the history and physical examination, 12-lead electrocardiogram, quality of life, adverse effects, and other medications.

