- b. If it is thought that medical care can be improved by knowledge of the treatment, that decision can be discussed with [name] at the Coordinating Center. It may be possible for a physician who does not see study patients to be unblinded, and advice regarding such care could be made by this physician after determining the therapy. This physician should avoid disclosing the study drug identity to other staff or to the patient's personal physician.
- c. If the decision is made that the patient's best interest requires that the Clinical Center staff have knowledge of the study drug, either directly or indirectly through advice of the physician mentioned in (b.) above, the patient will be considered to be on individualized therapy from that point on. It will usually be unnecessary for all staff to be unblinded. The staff that are unblinded are urged to preserve the confidentiality of the information.
- d. Regardless of the nature and degree of unblinding, the patient should continue to be followed on the usual visit schedule for the duration of the study. If at all possible, since analysis will be by intention to treat, the individualized therapy should be the study drug.
- e. Unblinding can be done by:
 1. On working days, between the hours of 8:00 am and 5:00 pm Pacific Time, a call should be placed to the Coordinating Center. If a physician other than a CAST investigator will break the blind, it is preferable for the coordinator or CAST investigator to call ahead and alert the Coordinating Center for the expected call if this is possible. The caller should have the patient I.D. number.

The phone number to call is [contact].

2. At other times, the Drug Distribution Center's 24-hour answering service can be called. The caller should ask for the pharmacist on call for the Cooperative Studies Program Research Pharmacy, identify the CAST study, and have the patient I.D. number or X-bottle number.

The phone number to call is [contact].

3. If necessary, the unblinding envelopes, which will be maintained at each center, may be opened to provide the information. In this case, the opened envelope, with information on the unblinding (reason unblinded, date unblinded) should be sent to the Coordinating Center. (At the end of the study all unblinding envelopes must be accounted for and all opened envelopes must be explained.)

f. Every case of unblinding must be reported to the Coordinating Center.

E. Confidentiality

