Power considerations are detailed below. These are based primarily on estimates available in CAST. They ignore the problem of dropout and dropin which (in CAST) have so far proven to be small.

The primary endpoint continues to be arrhythmic death or cardiac arrest in patients whose arrhythmias are suppressed by antiarrhythmic drugs. Total mortality is a secondary endpoint. The expected number of patients to be titrated, the expected number of patients to be suppressed or partially suppressed and the primary event rates are presented in the following tables.

Survival Rates To Arrhythmic Death/CA
in CAST Placebo-Patients

Patients with VPD's Suppressed, enrolled within 90 days of MI and	Event Rate			
	3 mos	6 mos	9 mos	12 mos
EF < 30	2.0%	5.3%	6.7%	10.1%
30 ≤ EF ≤ 40	0.5%	1.7%	1.7%	3.0%

Expected Enrollment and Rates based on past data and 33 months (4/1/89-12/30/91) of recruitment

Category of Patient	Titration		Blinded Therapy				
	N	2 week Dth/CA rate	Mor. Supp. Rate \geq 80%	Main Study-Mor Arm		Partially Suppressed Substudy ²	
				N	Prim Event Rate 1 yr overall	N	Prim Event Rate 1 yr overall
"Old CAST type pts \leq 90 days" (43.5 mos fu) ¹							
EF < 30	747	4.6%	55%	411	9.7%	168	10%
EF \geq 30 - \leq 40	859	1.7%	65%	559	2.2%	150	5%
							23.1%
							11.6%
"higher risk pts because change in VT and age" (avg 43.5 mos fu)							
EF < 30	100	5%	55%	55	11%	23	12%
EF \geq 30 - \leq 40	100	2%	65%	65	2.5%	18	6%
							27.8%
							13.9%
"old CAST ENC/FLEC pts (avg 54 mos fu) assuming 75% eligible and willing"							
EF < 30	106	1%	80%	85	5%	11	6%
EF \geq 30 - \leq 40	285	5%	80%	228	1%	29	1.5%
							16.5%
							4.2%
"old MOR pts (avg 60 mo fu) Main Study Substudy							
	2197			272	7.2%	43	10%
							30%
TOTAL				1675		442	
Average Event Rate		2.7%			12.9%		18.3%
Power	.72	(a .05 1 sided test and $\lambda = .5$)		.73	(a 1 sided 0.025 test and $\lambda = .7$)	.28	(a .05 1 sided test and $\lambda = .8$)

1 Assumes recruitment at approximately 1.2 times the rate in the 12 months prior to May 1989.

2 Assumes 50% of the patients not suppressed will be partially suppressed.

a) The main study (Primary analysis-- moricizine suppressed patients). As before, the design of CAST will be a one-sided study testing for benefit with alpha level 0.025.

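### Trial data collection stops after a resuscitated cardiac arrest, so the two mortality endpoints as worded would miss later deaths, more of them in the arm with more arrests

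*Protocol*

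**What the plan says.** Section 9 lists three events that lead to permanent withdrawal of study drug. For the first, resuscitated cardiac arrest or ventricular fibrillation, the site completes the Death or Cardiac Arrest form, and then "no additional study followups need be scheduled and no further CAST data should be collected". For the other two, disqualifying ventricular tachycardia and symptomatic unsustained ventricular tachycardia, follow-up continues.

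Other parts of the protocol bear on this:

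- Section 2.D counts resuscitated ventricular fibrillation (or undocumented resuscitated arrest) as a primary event. It lists "total cardiac mortality" and overall mortality from any cause as secondary endpoints.
- Section 2.E keeps all patients in follow-up until a single closing date.
- The end of section 9 says: "In addition, a patient advanced to individualized therapy will still be followed per protocol".
- Section 11.D, item 2.d, says that whatever the degree of unblinding, "the patient should continue to be followed on the usual visit schedule for the duration of the study", and gives the intention-to-treat analysis as a reason for what follows.
- The 1989 revision states that nothing changes beyond its listed items, and none of them touches this rule. Item 11 repeats: "Total mortality is a secondary endpoint". Item 6e sets up telephone contact every six months, with event data, for patients who are not rerandomized.

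**The concern.** The rule stops observation because of an outcome that the drug is meant to change. For the primary endpoint this is harmless, since the arrest is already the patient's first event. It is not harmless for mortality. An arrest survivor is alive, and a death a month or a year later belongs in both mortality endpoints as section 2.D words them. Under section 9 that death has no route into the trial data.

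Total mortality is the natural check on a cause-specific primary endpoint, and section 5.B.4 itself allows that drug therapy may increase fatal arrhythmias. An analysis plan cannot repair the gap afterwards, because the data would never have been collected. Cardiac mortality also needs a cause of death that the blinded Events Subcommittee can review.

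**Working it through.** **1. Reproduce the plan's own figure.** Revision item 11 gives 1675 main-study patients, a 12.9% event rate, a 30% reduction, one-sided alpha 0.025 and power of about .73.

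- Two proportions: 1675 / 2 = 837.5 per arm, 12.9% against 0.7 × 12.9% = 9.03%. Power = 0.718.
- Event-driven (Schoenfeld): 1675 × 0.129 = 216 events, hazard ratio 0.7. Power = 0.746.

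The stated .73 lies between these. It concerns the primary endpoint and is not in dispute. The planning inputs can be used for what follows.

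**2. Expected primary events.** Placebo: 837.5 × 0.129 = 108.04. Active: 837.5 × 0.0903 = 75.63.

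**3. Deaths lost.** Two quantities are not in the documents and are assumed: *f*, the share of primary events that are resuscitated arrests (10–30%), and *m*, the share of those patients who die later in the study (20–60%). Deaths lost per arm = events × *f* × *m*.

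| *f* | *m* | Placebo lost | Active lost |
|---|---|---|---|
| 10% | 20% | 2.2 | 1.5 |
| 20% | 40% | 8.6 | 6.1 |
| 30% | 60% | 19.4 | 13.6 |

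**4. Direction.** If *f* and *m* are similar in the two arms, lost deaths follow the ratio of primary events. Under the design hypothesis, placebo loses more. In the interim table (revision item 1), arrhythmic death or arrest was 33/730 on encainide or flecainide and 9/725 on placebo, a ratio of 3.64, so there active loses more. In both cases the absolute mortality difference shrinks.

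**5. Size of the bias.** The documents give no planned total of deaths, so the shift cannot be computed for the revised design. The interim table gives an illustration. Its totals of 56 and 22 combine deaths and arrests. Take arrests as 33*f* and 9*f*.

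- Deaths recorded under the rule: 56 − 33*f* and 22 − 9*f*.
- All deaths: add back 33*fm* and 9*fm*.

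| *f* | *m* | All deaths, active / placebo | Risk ratio, all deaths | Recorded deaths, active / placebo | Risk ratio, recorded |
|---|---|---|---|---|---|
| 10% | 20% | 53.36 / 21.28 | 2.49 | 52.7 / 21.1 | 2.48 |
| 20% | 40% | 52.04 / 20.92 | 2.47 | 49.4 / 20.2 | 2.43 |
| 30% | 60% | 52.04 / 20.92 | 2.47 | 46.1 / 19.3 | 2.37 |

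Worked for the last row: (52.04/730) / (20.92/725) = 2.47, and (46.1/730) / (19.3/725) = 2.37. The shift is about 0.01 to 0.10, always toward 1.

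**The case against.** **An arrest may already count in the mortality totals.** Section 2.D treats a resuscitated arrest as an arrhythmic death, one form serves both death and arrest, and the total column of the interim table combines mortality with cardiac arrest. On that reading no later death is lost. This cannot be dismissed, because the protocol does not say which reading applies. But sections 2.D and revision item 11 name mortality without arrest, and a composite would not be the endpoint they describe. The ambiguity itself needs settling.

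**Deaths could be found elsewhere.** Section 11.E sends identifiers to the Coordinating Center for National Death Index searches. A reader might infer that every death after an arrest is irretrievable; the documents do not support that. They describe the searches as future long-term follow-up, however, and do not make them a source for the trial endpoints.

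**Item 6e may already cover some of these patients.** It makes no exception for a prior arrest, so survivors in the encainide and flecainide cohort may be reached. The remaining gap is then mainly in the moricizine comparison.

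**Event 1 is a deliberate exception.** A reader might infer a head-on contradiction with the end of section 9 and with section 11.D. The documents support only a partial one: event 1 does not assign patients to individualized therapy, and breaking the code after an arrest is reserved for necessity. Those rules conflict only for arrest patients who are in fact unblinded or moved to individualized therapy. Nor does "Primary analyses will be by intention to treat and will be one-sided, with an alpha value of 0.025" settle the matter, since it speaks of primary analyses. The conflict that stands without qualification is with section 2.E.

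**Conclusion.** The point holds in a limited form. Section 9, event 1, cannot be squared with follow-up of all patients to a common date. Total cardiac and total overall mortality, as worded, would miss deaths after an arrest, and more of them in the arm with more arrests. In the revised design that is about 2–19 placebo and 1.5–14 active deaths. This assumes 10–30% of primary events resuscitated and 20–60% of those patients dying later, with both shares similar across arms.

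It would be wrong to infer that the mortality results are heavily distorted or that the primary result is at risk. The interim illustration shows a modest pull toward no effect. It comes from a comparison that was stopped after roughly 300 days of average exposure, so it indicates scale only. The primary endpoint, its alpha and power, and the endpoint combining sustained ventricular tachycardia with arrhythmic death are untouched. This should be fixed because the gap is explicit and cheap to close, not because the bias is shown to be large.

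**What to change.** 1. Replace the sentence in section 9, event 1, so that vital status, date of death and cause of death are collected for every randomized patient to the common termination date, including after a resuscitated arrest. The six-monthly telephone contact of revision item 6e can carry this.
2. Obtain vital status, and date and cause of any death, for patients already closed out under the present rule.
3. State whether the two mortality endpoints count a resuscitated arrest, so that sections 2.D, revision item 11 and the interim table's total column agree. If National Death Index searches are to supply endpoint deaths, say so.

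The cost is a sentence or two of protocol text and occasional telephone calls. With *f* at 10–30%, the number of patients concerned in the revised main study is about 18 (10.8 + 7.6) to 55 (32.4 + 22.7). Sample size, alpha and primary power do not change. The change concerns data collection only and leaves treatment after the event as it is.
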